#### Primary analysis for the second supplementary estimand

Missing data at Week 16 independent of the pandemic will be imputed using MI (100 iterations) assuming MAR within 4 groups defined according to treatment group and whether the subject has experienced an IE (independent of the pandemic).

Missing data or 'treated as missing' data at Week 16 due to the pandemic will be imputed using MI assuming MAR within treatment group using data from subjects who have not experienced an IE.

Page 113 of 157

For each of the 100 imputed datasets, the difference in response rates will be analysed using the CMH test stratified by region and baseline IGA-CHE score. The results of the analyses will be combined using Rubin's rule to provide the estimated treatment difference and associated standard error, and the 95% CI for the treatment difference will be calculated.

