# 14.3.6 Estimand strategy

### 14.3.6.1 Overview

The analysis of endpoints related to efficacy and health-related quality of life will be based on the FAS.

The following primary and supplementary estimands will be defined for binary and continuous endpoints (primary and key secondary endpoints).

The primary estimand will use a 'composite' strategy to handle IEs. With a 'composite' strategy, the occurrence of an IE is a component of the endpoint (see also Section 5.3).

A first supplementary estimand will use a 'pandemic modified composite' strategy. The strategy follows a 'composite' strategy for IEs independent of the COVID-19 pandemic. However, data collected after the IE related to the pandemic will be 'treated as missing' and imputed assuming MAR.

A second supplementary estimand will use a 'treatment policy' strategy which attempts to quantify the effect of the randomised treatment, ignoring the occurrence of IEs. Data collected for the endpoint of interest are used regardless of whether an IE (independent of the pandemic) occurred. Data collected after an IE related to the pandemic will be 'treated as missing' and imputed assuming MAR. This second supplementary estimand will be used for endpoints related to Week 16 (primary endpoint visit).

For the 'composite' and 'treatment policy' estimands, pre-specified sensitivity analyses will be conducted to assess the robustness of the results with respect to the handling of missing data.

The primary estimand for 'time-to-event' endpoints (exploratory endpoints) will use a 'while on treatment' strategy. Under the 'while on treatment' strategy, the actual duration of treatment is not important for determining treatment benefit. The interest lies in assessing the treatment response prior to the occurrence of IEs. This strategy will be implemented to handle IEs for time-to-event endpoints.

Analysis to summarise and assess the effect of patterns of missing data related to the pandemic will be specified in the statistical analysis plan prior to breaking the randomisation code.

Page 107 of 157

The following IEs are considered to affect the interpretation of the estimated treatment effects:

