- Initiation of rescue treatment: This IE occurs when a subject initiates rescue treatment. This IE can occur at the discretion of the investigator. If rescue treatment is initiated, regardless of relatedness to the COVID-19 pandemic, the subject must stop treatment with IMP immediately and will not be allowed to restart treatment with IMP (refer to Section 9.5 for details). This IE is handled without assessing relatedness to the pandemic.
- Permanent discontinuation of IMP independent of the COVID-19 pandemic: This IE occurs when a subject permanently discontinues IMP independent of the pandemic. This IE can occur at the subject's own initiative, at the discretion of the investigator or the sponsor, or if the subject is lost to follow-up.
- Permanent discontinuation of IMP related to the COVID-19 pandemic: This IE occurs when a subject permanently discontinues IMP due to circumstances related to the pandemic; not attributed to lack of efficacy or randomised treatment features considered unacceptable by the subject.

Panel 23 presents an overview of how observed and missing data will be handled according to the IEs for the primary analysis for estimands.

 Trial ID: LP0133-1402
 Date: 20-Aug-2021
 Version: 4.0, Final

 Page 108 of 157
 Page 108 of 157

Panel 23: Handling of observed and missing data according to the intercurrent events for the primary analysis for estimands

		Estimand strategy for binary endpoints			Estimand strategy for continuous endpoints		
Intercurrent event	Data observed or missing	Composite (Primary)	Pandemic modified composite (First supplementary)	Treatment policy (Second supplementary)	Composite (Primary)	Pandemic modified composite (First supplementary)	Treatment policy (Second supplementary)
Initiation of rescue treatment 	Observed	Non-response	Non-response	Value will be used as observed	WOCF (including baseline value)	WOCF (including baseline value)	Value will be used as observed
	Missing	Non-response	Non-response	MI (MAR)	WOCF (including baseline value)	WOCF (including baseline value)	MI (MAR)
Permanent discontinuation of IMP independent of the	Observed	Non-response	Non-response	Value will be used as observed	WOCF (including baseline value)	WOCF (including baseline value)	Value will be used as observed
pandemic	Missing	Non-response	Non-response	MI (MAR)	WOCF (including baseline value)	WOCF (including baseline value)	MI (MAR)

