## Primary analysis for the first supplementary estimand

Missing data for subjects who do not attend the visit for the endpoint of interest and do not experience IEs prior to this visit will be imputed as non-response, unless data is missing due to the pandemic in which case it will be imputed assuming MAR.

The procedure for imputing values will be implemented in a 2-step procedure, where all missing or 'treated as missing' data will be imputed using MI (100 iterations) assuming MAR within treatment groups. Once the 100 complete data sets have been generated by MI, non-responder imputation of relevant data points not affected by the pandemic will be applied according to the rules described above.

For each of the 100 complete datasets, the difference in response rates will be analysed using the CMH test stratified by region and baseline IGA-CHE score. The results of the analyses will be combined using Rubin's rule to provide the estimated treatment difference and associated standard error, and the 95% CI for the treatment difference will be calculated.

Second supplementary estimand for endpoints at Week 16: 'treatment policy' strategy This supplementary estimand evaluates the treatment effect in adult subjects with moderate to severe CHE, regardless of initiation of rescue treatment or permanent discontinuation of IMP in a world without COVID-19 pandemic.

Observed data will be used in the analysis, including the data observed after the occurrence of IEs independent of the pandemic. To support the 'treatment policy' strategy, subjects who experience IEs prior to Week 16 will be asked to attend the primary endpoint visit at Week 16 for collection of data.

For subjects who experience an IE related to the pandemic prior to Week 16, observed data at Week 16 will be 'treated as missing' and imputed assuming MAR.

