#### Primary analysis for the first supplementary estimand

Missing data for subjects who do not attend the visit for the endpoint of interest and do not experience IEs prior to this visit will be imputed as WOCF (including the baseline value), unless data is missing due to the pandemic in which case it will be imputed assuming MAR.

The procedure for imputing values will be implemented in a 2-step procedure, where all missing or 'treated as missing' data will be imputed using MI (100 iterations) assuming MAR within treatment groups. WOCF imputation of relevant data points not affected by the pandemic will be applied according to the rules described above.

For each of the 100 complete datasets, the change (or percentage change) from baseline to the endpoint of interest will be analysed using the ANCOVA model with effects of treatment,

Page 115 of 157

region, baseline IGA-CHE score, and baseline value. The estimates and standard errors from the analyses will be combined using Rubin's rule to provide the estimate and associated standard error.

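### Treatment-policy estimand: as written, a Week 16 value lost to the pandemic after a non-pandemic intercurrent event is imputed from same-arm subjects with no intercurrent event (minor correction)

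*Combined protocol and SAP*

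**What the plan says.** The second supplementary estimand is defined in Sections 14.3.6.2 (binary) and 14.3.6.3 (continuous) as the effect "regardless of initiation of rescue treatment or permanent discontinuation of IMP in a world without COVID-19 pandemic". Section 14.3.6.1 adds: "Data collected for the endpoint of interest are used regardless of whether an IE (independent of the pandemic) occurred".

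The primary analysis for this estimand has two imputation rules, which are separated by why the Week 16 value is missing:

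- When the loss has nothing to do with the pandemic, multiple imputation (MI) is done "within 4 groups defined according to treatment group and whether the subject has experienced an IE (independent of the pandemic"), so donors share both the arm and the IE status of the subject being imputed.
- The other rule has this scope: "Missing data or 'treated as missing' data at Week 16 due to the pandemic". Here each arm has a single donor pool, and the method is "MI assuming MAR within treatment group using data from subjects who have not experienced an IE".

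The binary and continuous sections carry both rules. The second rule's donor clause recurs in the sensitivity analysis for this estimand in each section.

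On rescue treatment, Section 14.3.6.1 states: "This IE is handled without assessing relatedness to the pandemic". Rescue therefore always counts as a non-pandemic IE.

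**The concern.** The second rule selects donors by the reason for missingness and sets no condition on the IE status of the subject being imputed. Consider a subject who starts rescue, or stops IMP for a non-pandemic reason, and whose Week 16 assessment is then lost to the pandemic. In a world without the pandemic that IE would still have happened, and the target keeps the outcome that follows it. The rule as written instead draws the value from subjects who never had an IE.

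If Week 16 response differs by IE status, part of an estimate meant to hold regardless of IEs becomes an estimate as if there had been none. Two programmers, one following the text and one following the layout of Panel 23, could also obtain different results.

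**Working it through.** **Can the case arise?** Yes. Section 14.3.1 notes that data can be missing because of the pandemic without a pandemic-related IE. Section 10.3 asks subjects who stop IMP to return at Week 16, so that visit can be lost. Appendix 7 says that phone or video visits give no investigator efficacy assessments.

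**What happens to a subject with a non-pandemic IE?**

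| Week 16 value | Treatment under the text |
|---|---|
| Observed | Used as observed |
| Missing, not pandemic | Imputed from same-arm subjects with an IE |
| Missing, pandemic | Imputed from same-arm subjects with no IE |

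Only the third row departs from the target.

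**Do other passages correct it?**

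- Panel 23 classifies by IE first. It splits missing data by pandemic cause only in the block without IEs. For rescue and non-pandemic discontinuation it says MI under MAR and names no donors.
- Panel 24 conditions on IE occurrence only for pandemic-independent data.
- For the first supplementary estimand the pandemic exception is confined to subjects who "do not experience IEs prior to this visit will be imputed as non-response, unless data is missing due to the pandemic" (binary) or who "do not experience IEs prior to this visit will be imputed as WOCF (including the baseline value") (continuous). The second supplementary estimand has no such limit.

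**Size.** The plan has no figure on this point. Its nearest figure, power of at least 99% (Section 14.1), reproduces: 300 vs 150 subjects, 40% vs 10%, one-sided 2.5% gives more than 99.99%. This issue does not touch it.

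From Section 14.1: 450 subjects randomised 2:1, so 300 and 150; response 40% and 10%.

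Assumed, because the documents give no values: IE rates of 10% (delgocitinib) and 20% (vehicle); m = 10% of those Week 16 values lost to the pandemic; response by IE status as tabulated.

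- Affected subjects: 300 x 0.10 x 0.10 = 3 and 150 x 0.20 x 0.10 = 3.
- Shift (as written minus IE-matched) = IE rate(delgocitinib) x m x (no-IE minus IE response) - IE rate(vehicle) x m x (no-IE minus IE response). The weights are 0.10 x 0.10 = 0.010 and 0.20 x 0.10 = 0.020.

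| Delgocitinib no-IE / IE (%) | Vehicle no-IE / IE (%) | Shift (points) |
|---|---|---|
| 45 / 45 | 12 / 5 | 0.010 x 0 - 0.020 x 7 = -0.14 |
| 45 / 45 | 12 / 12 | 0.00 |
| 45 / 20 | 12 / 5 | 0.010 x 25 - 0.020 x 7 = +0.11 |
| 45 / 20 | 12 / 25 | 0.010 x 25 + 0.020 x 13 = +0.51 |
| 45 / 10 | 10 / 35 | 0.010 x 35 + 0.020 x 25 = +0.85 |

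The 45% and 12% inputs fit the planning rates if those are read as composite rates: 45 x 0.90 = 40.5 and 12 x 0.80 = 9.6.

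Half-width of the 95% CI: 1.96 x sqrt(0.4 x 0.6/300 + 0.1 x 0.9/150) = 1.96 x 0.0374 = 7.3 points. The largest tabulated shift is 0.85/7.3 = 12% of it.

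The shift is proportional to m. With IE rates of 15% and 30% and m = 20%, the extreme patterns give 0.03 x 0 - 0.06 x 7 = -0.42 and 0.03 x 35 + 0.06 x 25 = +2.55. The latter needs every extreme input at once and implies composite rates below the planning values (45 x 0.85 = 38%; 10 x 0.70 = 7%).

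These figures use marginal donor rates. MI would normally also use the subject's own earlier scores. If those closed half the gap (a further assumption), each shift would halve, for example 0.51 x 0.5 = 0.26.

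**The case against.** The strongest reply is that an IE-first order is already in the plan. Section 14.3.1 refers to Panel 23 for how data are handled by IE and pandemic relatedness, and Panel 23 does not split missing values by cause once a rescue or non-pandemic discontinuation has occurred. On that reading the no-IE donor rule covers only subjects with a pandemic-related IE and no-IE subjects who missed the visit, and no-IE donors suit both. This may well be the intent. It does not cure the text, because Panel 23 names no donors and the only passages that do name them make no such restriction.

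Panel 24 is weak evidence for either side. Its shorthand, taken literally for the first supplementary estimand, would send a rescued subject with a pandemic-missed visit to MI, where Panel 23 requires non-response.

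The separately finalised SAP foreseen in Section 14.3.14 may settle the matter. The text reviewed here does not.

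A reader might infer more than the documents support:

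- That the rule favours delgocitinib. The sign depends on response by IE status, which is not given. Section 5.3 expects IEs to stem mostly from lack of efficacy or unacceptable treatment features. Worse response in both arms is therefore at least as natural as the +0.51 pattern, and gives +0.11.
- That the handling of pandemic-related discontinuation is wrong. Treating later data as missing and using no-IE donors fits a target without the pandemic.
- That exempting pandemic-missing data from non-response or copy-reference in the sensitivity analyses is an error. It is a stated choice.

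**Conclusion.** The concern holds as a minor error of wording: the stated donor rule misdirects a small, identifiable group of subjects, and Panel 23 only hints at a better intent. At the assumed 10% and 20% IE rates with 10% of those visits lost, the shift is about -0.1 to +0.9 points. It could be larger only with more IEs or more lost visits, and would be smaller if earlier scores inform the imputation.

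The exposure is mainly in the 4 of 12 Week 16 endpoints that need a site visit (IGA-CHE TS, HECSI-75, HECSI-90 and percentage change in HECSI); the six HESD and two DLQI endpoints can be collected remotely under Appendix 7. It would be wrong to conclude that the trial's main result is at risk: Section 14.3.5 bases confirmatory testing on the primary analysis of the primary estimand, which this rule does not enter. Confidence is medium, because the intended reading and all the rates are unknown.

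**What to change.** In the primary analysis for the second supplementary estimand, in both Sections 14.3.6.2 and 14.3.6.3 (or in the SAP before the randomisation code is broken, Section 14.3.14), state:

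- For subjects with a non-pandemic IE (any rescue included) and no pandemic-related IE, missing Week 16 values are imputed within the existing treatment-by-IE groups, whatever the reason for missingness.
- The no-IE donor rule applies to subjects with no IE whose value is missing because of the pandemic, and to subjects whose only IE is pandemic-related.

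Add the donor group to Panel 23 and align Panel 24. The sponsor should also state which rule applies in the two sensitivity analyses, and for subjects who have both a pandemic-related IE and rescue. These are the sponsor's choices and the documents do not settle them.

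The cost is one or two sentences per section, notes to two panels and one grouping variable in the imputation code. No new data are needed, and the primary analysis and testing procedure do not change. The IE donor pool is small (in the illustration at most 30 x 0.9 = 27 per arm), but the four-group rule already relies on it. If the IE-first reading was always meant, the edit only writes it down.

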### Sensitivity analysis for the second supplementary estimand

Missing data at Week 16 will be imputed as non-response, unless data is missing or 'treated as missing' due to the pandemic in which case it will be imputed using MI (100 iterations) assuming MAR within treatment group using data from subjects who have not experienced an IE.

The difference in response rates will be analysed as described above for the primary analysis for the second supplementary estimand.

# 14.3.6.3 Estimand strategy for continuous endpoints

The population level summary will be the difference in mean change (or percentage change) from baseline to the endpoint of interest between delgocitinib cream 20 mg/g and cream vehicle.

## Primary estimand: 'composite' strategy

This primary estimand evaluates the treatment effect in adult subjects with moderate to severe CHE, without initiation of rescue treatment or permanent discontinuation of IMP.

For subjects who received rescue treatment or who have permanently discontinued IMP prior to the endpoint of interest, observed data after the IEs will be considered non-response by using WOCF (including the baseline value).

### Primary analysis for the primary estimand

Missing data for subjects who do not attend the visit for the endpoint of interest and do not experience an IE prior to this visit will be imputed as WOCF (including the baseline value).

The change (or percentage change) from baseline to the endpoint of interest will be analysed using an ANCOVA model with effects of treatment group, region, baseline IGA-CHE score, and baseline value (endpoint of interest).

Page 114 of 157

### Sensitivity analysis for the primary estimand

Missing data at the endpoint of interest, for subjects who did not experience IEs prior to that, will be handled as follows:

- For subjects in the delgocitinib cream 20 mg/g group, missing data will be imputed as WOCF (including the baseline value).
- For subjects in the cream vehicle group, missing data will be imputed using MI (100 iterations) assuming MAR.

For each of the 100 complete datasets, the change (or percentage change) from baseline to the endpoint of interest will be analysed using the ANCOVA model with effects of treatment, region, baseline IGA-CHE score, and baseline value. The estimates and standard errors from the analyses will be combined using Rubin's rule to provide the estimate and associated standard error.

# First supplementary estimand: 'pandemic modified composite' strategy

This first supplementary estimand evaluates the treatment effect in adult subjects with moderate to severe CHE, without initiation of rescue treatment or permanent discontinuation of IMP in a world without COVID-19 pandemic, where interest lies in the treatment effect as it would have been observed had the COVID-19 pandemic not happened.

For subjects who experience IEs independent of the pandemic prior to the endpoint of interest, observed data after the IEs will be considered non-response by using WOCF (including the baseline value).

For subjects who experience an IE related to the pandemic prior to the endpoint of interest, observed data after the IE will be 'treated as missing' and imputed assuming MAR.

#### Primary analysis for the first supplementary estimand

Missing data for subjects who do not attend the visit for the endpoint of interest and do not experience IEs prior to this visit will be imputed as WOCF (including the baseline value), unless data is missing due to the pandemic in which case it will be imputed assuming MAR.

The procedure for imputing values will be implemented in a 2-step procedure, where all missing or 'treated as missing' data will be imputed using MI (100 iterations) assuming MAR within treatment groups. WOCF imputation of relevant data points not affected by the pandemic will be applied according to the rules described above.

For each of the 100 complete datasets, the change (or percentage change) from baseline to the endpoint of interest will be analysed using the ANCOVA model with effects of treatment,

Page 115 of 157

region, baseline IGA-CHE score, and baseline value. The estimates and standard errors from the analyses will be combined using Rubin's rule to provide the estimate and associated standard error.

## Second supplementary estimand for endpoints at Week 16: 'treatment policy' strategy

This supplementary estimand evaluates the treatment effect in adult subjects with moderate to severe CHE, regardless of initiation of rescue treatment or permanent discontinuation of IMP in a world without COVID-19 pandemic.

Observed data will be used in the analysis, including the data observed after the occurrence of IEs independent of the pandemic. To support the 'treatment policy' strategy, subjects who experience IEs prior to Week 16 will be asked to attend the primary endpoint visit at Week 16 for collection of data.

For subjects who experience an IE related to the pandemic prior to Week 16, observed data at Week 16 will be 'treated as missing' and imputed assuming MAR.

### Primary analysis for the second supplementary estimand

Missing data at Week 16 independent of the pandemic will be imputed using MI (100 iterations) assuming MAR within 4 groups defined according to treatment group and whether the subject has experienced an IE independent of the pandemic.

Missing data or 'treated as missing' data at Week 16 due to the pandemic will be imputed using MI assuming MAR within treatment group using data from subjects who have not experienced an IE.

For each of the 100 complete datasets, the change (or percentage change) from baseline to Week 16 will be analysed using an ANCOVA model with effects of treatment, region, baseline IGA-CHE score, and baseline value. The estimates and standard errors from the analyses will be combined using Rubin's rule to provide the estimate and associated standard error.

### Sensitivity analysis for the second supplementary estimand

Missing data at Week 16 independent of the pandemic will be imputed using a pattern-mixture model where data in the delgocitinib cream 20 mg/g group as well as the cream vehicle group will be imputed from the cream vehicle group (copy-reference approach). The data will be imputed using MI (100 iterations) assuming MAR within 2 groups: subjects in the cream vehicle group who have experienced an IE independent of the pandemic, and subjects in the cream vehicle group who have not experienced an IE.

Page 116 of 157

Missing data or 'treated as missing' data at Week 16 due to the pandemic will be imputed using MI assuming MAR within treatment group using data from subjects who have not experienced an IE.

For each of the 100 completed datasets, the change (or percentage change) from baseline to Week 16 will be analysed using an ANCOVA model with effects of treatment, region, baseline IGA-CHE score, and baseline value. The results of the analysis will be combined using Rubin's rule to provide the estimate and associated standard error.

